## **Introduction**

### **Scientific background and explanation of rationale.**

Osteoarthritis (OA) of the knee is a chronic disease characterized by pain, reduced range of motion, instability and effusion in the joint. The weakness of the quadriceps as well as the hip muscles are commonly seen symptoms (1). Although the primary effects of the disease occur in articular cartilage; osteophytes, subchondral sclerosis, and cyst formation are concomitant complications to cartilage degradation (2). Progressive deterioration of the joint and chronic pain limit to perform knee functions, which result with a decline in quality of life in knee OA patients.

Physical therapy applications, exercise therapy, pharmacological treatments and intra-articular injections are considered as effective methods to relieve the symptoms of knee OA patients (3). Recently, Platelet-rich Plasma (PRP) treatment has received much attention for its use in the treatment of knee OA (4, 5). It has been shown that PRP injection would reduce pain and improve knee functions in patients with knee OA in the available literature, but some studies are underpowered or unblinded, thus the findings have low reliability. A number of systematic reviews and meta-analyses' evidence have not been exactly comprehensive and are even sometimes controversial (6-9). Because previous studies differed in the concentrations of leucocytes used for the preparation (11) SEP of PRP, dosage schedules, and so on. Moreover, no study has investigated the effect of PRP in comparison with that of a placebo injection in the same patient with bilateral knee OA. It is of interest to examine the effect of PRP in the same patient with bilateral OA.

After PRP injection, patients with knee OA are recommended to exercise.(16). It is thought that home exercises combined with PRP treatment may be an effective approach in the treatment of knee OA, but the importance of performing exercise program under the supervision of a

physiotherapist is emphasized (16). Isokinetic training under the supervision of a physiotherapist had significant effects on pain, function and muscle strength in OA patients after PRP injection (17). However, the combination of PRP injection and exercise therapy under the guidance of a physiotherapist has yet to be established.

### **Specific objectives or hypotheses**

The purpose of this study was to compare the effectiveness of supervised physiotherapy and home exercises after PRP injection in patients with knee OA. We hypothesized that the supervised physiotherapy program would be more effective in decreasing pain and improving muscle strength, physical function, and quality of life than home exercises following PRP injection in patients with knee OA.

### **Methods**

#### **Description of trial design (such as parallel, factorial) including allocation ratio**

This will be a randomized allocation ratio 1:1, controlled study conducted in the Hacettepe University, Turkey.

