#### **Eligibility criteria for participants.**

Inclusion Criteria:

- PRP injection due to knee OA,
- The PRP injection is given at least three days ago,
- 45- 70 years old
- Grade 2-3 according to Kellgren Lawrence osteoarthritis classification

Exclusion Criteria:

- Being male
- Have a neurologic, oncologic and/or rheumatologic disease

- Having any intra-articular application and / or physiotherapy and rehabilitation in the last 6 months,
- Have any other orthopedic problems involving the lower extremities
- having cognitive problem

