### **Outcome Measures**

### **Participants and Methods**

A randomized control clinic study design was used for the present study. A sample size calculation was conducted using G\*power (v3.1.9.2, Heinrich-Heine-University, Dusseldorf, Germany). An estimated more than 2-point pain level changes on VAS between pre- and posttreatments for repeated measures analysis, a power of 0.80, a  $\alpha$  of 0.05 and a total sample size of 28 knee OA patients need to be included in the present study.

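### Allocation is described only as randomised 1:1; sequence restriction and concealment are not specified, so the plan permits foreseeable assignments in an open trial of 28 patients

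*Combined protocol and SAP*

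**What the plan says.** The trial design section states: "This will be a randomized allocation ratio 1:1, controlled study". The Participants and Methods section adds only "A randomized control clinic study design was used for the present study" and the size: "a total sample size of 28 knee OA patients need to be included in the present study". No section says how the sequence is generated, whether it is simple or blocked, whether it is stratified, who holds it, who enrols patients, or how the next assignment is kept from that person.

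Four other places bear on the point:

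- **Eligibility criteria.** Severity enters as "Grade 2-3 according to Kellgren Lawrence osteoarthritis classification", so the grade has to be known for every patient at entry. One exclusion reads "Have any other orthopedic problems involving the lower extremities"; another concerns cognition. Neither has a threshold or a test.
- **Specific objectives or hypotheses.** The hypothesis is directional and favours supervised physiotherapy.
- **Interventions.** One arm exercises with a physiotherapist and the other at home with weekly telephone calls. There is a first evaluation before supervised exercise starts and a second at six weeks, all by one physiotherapist. Blinding is not mentioned, and neither is whether assignment comes before or after the first evaluation.
- **Statistical Analysis.** A two-way repeated-measures analysis compares the arms over the six weeks. KL grade is not in it, and no other covariate is named.

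**The concern.** Randomisation removes selection bias only if the person entering patients cannot foresee the next assignment. Here that person is not identified and no concealment is described. Patients and the treating physiotherapist must know the arm, so earlier assignments are likely to be visible in the department. The two exclusions above rest on judgement. Someone who foresaw the next assignment could, without breaking any written rule, find a borderline patient eligible or not according to the arm that was due. Such a choice can act on prognosis that is never measured, so adjustment for recorded baseline variables would not remove it.

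A second, smaller matter is chance. With 28 patients, an unrestricted sequence can leave the arms unequal in size or in KL grade, and the analysis as written makes no use of the grade.

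**Working it through.** **The plan's own figure.** The total of 28 (14 per arm) is given with power 0.80, alpha 0.05 and this effect: "An estimated more than 2-point pain level changes on VAS between pre- and posttreatments for repeated measures analysis". No SD, correlation or effect size f is stated, so 28 can be neither reproduced nor refuted. Read as a 2-point difference between arms in a two-sided t test, it implies an SD of about 1.82. The power figures below need only the stated 80% at 14:14.

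**1. Arm sizes under simple randomisation.** The number in one arm is Binomial(28, 0.5).

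- P(exactly 14:14) = C(28,14)/2^28 = 40,116,600/268,435,456 = 0.149.
- P(16:12 or worse) = 2 × P(X ≤ 12) = 0.572.
- P(18:10 or worse) = 2 × P(X ≤ 10) = 0.185.

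**2. What unequal arms cost.** For a two-sample t test with 26 degrees of freedom, the noncentrality at a:b is the 14:14 value times √(4ab)/28. Power of 80% at 14:14 needs a noncentrality of 2.91.

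| Split | Factor | Power |
|---|---|---|
| 14:14 | 1.000 | 80.0% |
| 15:13 | 0.997 | 79.8% |
| 16:12 | 0.990 | 79.2% |
| 17:11 | 0.977 | 78.1% |
| 18:10 | 0.958 | 76.6% |

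Weighted by the binomial probabilities, average power is 78.5%, a loss of 1.5 points.

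**3. Imbalance in KL grade with 14:14 arms.** Assume 14 of the 28 are grade 3; the documents do not give the mix. If x grade-3 patients fall in one arm, the arms differ by |2x − 14|, which is 4 or more when x ≤ 5 or x ≥ 9. The probability is 2 × Σ C(14,x)²/C(28,14) over x = 0 to 5, that is 2 × 5,150,979/40,116,600 = 0.257. With 8 or 20 grade-3 patients it is 0.209.

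**4. How guessable a blocked list would be.** This matters for the choice of remedy. A recruiter who knows all earlier assignments can always guess the arm that is behind and toss a coin when they are level; no knowledge of block size is needed. In a block of 2m the expected number of correct guesses is m + ½[4^m/C(2m,m) − 1].

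- Size 2: 1 + ½(4/2 − 1) = 1.50.
- Size 4: 2 + ½(16/6 − 1) = 2.83.
- Size 6: 3 + ½(64/20 − 1) = 4.10.

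With the two sizes equally frequent, blocks of 2 and 4 give (1.50 + 2.83)/6 = 72% and blocks of 4 and 6 give (2.83 + 4.10)/10 = 69%, against 50% for simple randomisation. Avoiding blocks of 2 therefore helps only a little. The main protection is that eligibility and baseline are settled before the envelope is opened.

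**5. Steering.** No calculation is possible. The documents contain nothing on who recruits, what that person knows, or how prognosis varies among borderline patients.

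**The case against.** The strongest reply is that silence is not absence. A short protocol may leave out a method that was in fact sound, and nothing in the documents says that assignments were known in advance. This stands: the finding is that the method is not specified. A reader might infer that allocation was unconcealed or that the arms were steered, and the documents do not support that.

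Three further objections also stand.

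- **Chance imbalance does not undermine validity.** Under proper randomisation it is already allowed for in the standard error and the 5% level. The planned analysis also uses the first evaluation as a time point, so a KL effect that is the same at both visits cancels from the group-by-time interaction. Only the part that acts on change remains, together with the post hoc comparisons at single time points.
- **KL grade has no unique claim as a stratum.** Pain, strength, function and WOMAC are outcome measures, and the first evaluation is the natural place for their baseline values. Not stratifying 28 patients is a design choice and not an error.
- **Unequal arms cost little**, as the power table shows.

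A reader might also want a figure for the inflated false-positive rate. In a six-week-only t test with 14 per arm, a shift of 0.3 SD would take 5% to about 12%. But no document supports 0.3 SD or any other shift, and that test is not the planned analysis, so the figure says nothing about this trial.

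What the objections do not answer is the gap itself: the written plan would be satisfied by an open list.

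**Conclusion.** The concern holds as an omission that should be repaired. The protocol specifies a ratio and nothing that protects it, in a trial where the arms cannot be hidden from patients or the treating physiotherapist, the hypothesis is directional, and some exclusions rest on judgement. Selection at entry is the serious part, because no later analysis can undo it; its size is unknown. That the trial is open is inferred from the nature of the two programmes, since the documents do not mention blinding.

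The chance component is modest. The arm-size probabilities assume simple randomisation, which the plan permits but does not state. The 0.26 for KL grade assumes equal numbers of grades 2 and 3, and falls to 0.21 if 8 or 20 of the 28 are grade 3. These figures justify a cheap gain in precision and no doubt about validity.

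**What to change.** **Trial design section.** After the 1:1 ratio, state that:

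- the list is computer-generated in permuted blocks of randomly varying size, with the sizes not disclosed to recruiters and blocks of 2 avoided (for example 4 and 6);
- it is prepared by an existing department member who does not recruit, treat or assess trial patients;
- assignments are held in sequentially numbered, opaque, sealed envelopes, each opened only after eligibility is confirmed, the first evaluation is done and the patient is entered.

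**Statistical Analysis section.** Add KL grade (2 v 3) as a factor in the between-arm analysis. For it to bear on the group-by-time comparison, its interaction with time must be in the model. Leaving out a group-by-grade term keeps the cost to one degree of freedom (26 to 25 for error).

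**Optional.** Stratify the list by KL grade, with a separate envelope series for each grade.

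**Cost.** About an hour of preparation, one degree of freedom, and no extra patients or visits. The final split may be slightly unequal. With one list in blocks of 4 and 6, 28 patients can end no worse than 15:13. With two strata, each can stop up to 3 out of balance in a block of 6, so 17:11 is possible.

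**If enrolment is already complete.** The protocol mixes future and past tense, so this cannot be ruled out. In that case, report the method actually used for sequence generation and concealment, and apply only the analysis change.

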#### **Eligibility criteria for participants.**

Inclusion Criteria:

- PRP injection due to knee OA,
- The PRP injection is given at least three days ago,
- 45- 70 years old
- Grade 2-3 according to Kellgren Lawrence osteoarthritis classification

Exclusion Criteria:

- Being male
- Have a neurologic, oncologic and/or rheumatologic disease

- Having any intra-articular application and / or physiotherapy and rehabilitation in the last 6 months,
- Have any other orthopedic problems involving the lower extremities
- having cognitive problem

### **Methodology of the study**

Patients who underwent PRP injection for knee OA were included in the study. It will be noted that PRP injection to the patients is done by the same physician using the same PRP kit by the same method at the Hacettepe University Faculty of Medicine Department of Orthopaedics and Traumatology.

### **Outcome Measures**

### **Participants and Methods**

A randomized control clinic study design was used for the present study. A sample size calculation was conducted using G\*power (v3.1.9.2, Heinrich-Heine-University, Dusseldorf, Germany). An estimated more than 2-point pain level changes on VAS between pre- and posttreatments for repeated measures analysis, a power of 0.80, a  $\alpha$  of 0.05 and a total sample size of 28 knee OA patients need to be included in the present study.

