### **Pain Measurement**

Visual Analog Scale was used to assess the subjects' pain during rest and activity. A 10 cm line was drawn and subjects were wanted to mark the point (0; no pain, 10; worst imaginable pain) as representing the pain during rest and activity (18).

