### **Muscle Strength Measurement**

Quadriceps, hamstring muscles and the hip stability isometric test (HipSIT) strength were measured with a hand-held digital dynamometer (Lafayette Instrument Company, Lafayette). Each subject was verbally informed before the test in order to ensure correct movement and subjects were asked to perform submaximal contraction against the evaluator's hand before testing (19). "Break test" technique was performed for the strength measurement. According to this technique, the evaluator gradually overcomes the muscle strength and stops when the joint gives way (20). The quadriceps muscle strength was measured in a sitting position (Hip 90° flexion, knee extended) with hands crossed across the chest. The hand-held dynamometer was positioned on the anterior surface of the lower leg proximal to the ankle during test (21). Hamstring muscle group measurement was carried out on prone position (Hip neutral position, knee flexion 90°). The hand-held dynamometer was positioned on the posterior surface of the lower leg proximal to the ankle during test (21). The HipSIT evaluates the abductor, external rotator and extensor muscles of the hip together. This test was performed in a side-lying position (Hips 45° flexion, knees 90° flexion, heels in contact with the limb tested superior to opposing limb as 20° abduction). The hand-held dynamometer was placed on laterally positioned 5 cm above the knee joint interline during test (22). Each measurement for each muscle was performed 3 times at 30 sec intervals and the higher value was recorded. There was also a minute interval between muscle groups measurements.

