### **Interventions**

Each subject was informed about knee OA and daily activities that negatively affect the knee OA. They were also asked to use cold press 3 times (10-15 min) a day for 6 weeks. Supervised physiotherapy group performed exercises 3 times a week for 6 weeks under supervision of a physiotherapist after the first evaluation. The subjects in home exercise group were taught exercises and they were informed to do exercises 3 times a week for 6 weeks. Home exercise group was telephoned to motivate them to do exercise or to find out if they have any problem about the exercises once a week for 6 weeks. The exercise programs for each group consisted of these parts: warm up, strengthening, balance and cool down period (Appendix 1). The standard exercises were performed by all of the subjects in each group in order to standardize the exercise procedure. We used OMNI Resistance Exercise Scale for perceived effort to standardize elastic-band (Thera-Band; The Hygenic Corporation, Akron, OH) resistance among subjects (26). Subjects were asked to do 3 repetitions for each exercise starting with lowest resistance elastic band, and the resistance of the elastic band was increased until it reached 5 on the 11-point scale to determine the appropriate elastic band. Second measurements were performed at the end of 6 weeks, the day of routine doctor control for PRP injection. All assessments were performed by the same physiotherapist.

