### **Statistical Analysis**

A two-way repeated-measures analysis was initially used to investigate differences in the primary outcome variable (muscle strength) between the supervised physiotherapy group and home exercise group over 6- week period; followed by secondary outcomes measures (VAS, WOMAC ). In the occurrence of significant main or interaction effects, a Bonferroni post hoc correction was used to assess significant findings between the groups at specific assessment time points. Statistical analysis was performed using SPSS software (version 22.0). The significance level was set at an alpha of 0.05.

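### The only stated power (0.80 with 28 patients) is based on a VAS pain change, while the declared primary outcome is muscle strength compared between groups, for which no power is given

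*Combined protocol and SAP*

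**What the plan says.** The combined protocol and SAP has one sample-size statement, in Participants and Methods under Outcome Measures. It reads "An estimated more than 2-point pain level changes on VAS between pre- and posttreatments for repeated measures analysis, a power of 0.80", and goes on to an alpha of 0.05 and a total of 28. It gives no SD, no pre-post correlation, no standardised effect and no G*Power test option.

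The Statistical Analysis section assigns the roles differently. A two-way repeated-measures analysis is used to "investigate differences in the primary outcome variable (muscle strength) between the supervised physiotherapy group and home exercise group", "followed by secondary outcomes measures (VAS, WOMAC"). Post hoc comparisons follow "In the occurrence of significant main or interaction effects".

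Three other sections bear on the point:

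- **Hypothesis.** It is a between-group one: supervised physiotherapy "would be more effective in decreasing pain and improving muscle strength, physical function, and quality of life than home exercises". Pain comes first in that list, but nothing there is called primary.
- **Outcome measures.** Strength is three measures: "Quadriceps, hamstring muscles and the hip stability isometric test (HipSIT) strength were measured with a hand-held digital dynamometer". VAS is two scores, with the mark taken "as representing the pain during rest and activity". No single one is chosen in either case.
- **Timing.** There are two assessments, the first before the exercise programme and the other after it: "Second measurements were performed at the end of 6 weeks".

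**The concern.** A power figure describes one test on one outcome. Here it is attached to an outcome that the analysis section calls secondary, so the primary comparison has no stated sample-size basis. A reader who meets 0.80 and 28 will naturally take them to cover the primary test, and they do not. If the strength comparison is null, the plan offers no way to judge whether 28 patients could have shown a difference worth having.

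There may be a second mismatch. The 2 points are worded as a change from before to after treatment, while the trial asks whether one group changes more than the other. If the calculation was within-patient, 0.80 would not describe the group comparison even for VAS.

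This is a gap in justification and consistency. It does not by itself bias the estimate or raise the type I error rate.

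**Working it through.** **Inputs from the documents.** Power 0.80, total 28 and a VAS change of more than 2 points (Participants and Methods); alpha 0.05 (Statistical Analysis); 1:1 allocation (trial design), hence 14 per group; two time points (Interventions).

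**Assumptions.** Two-sided alpha, complete data, equal SDs at both times, exactly 2 points for VAS, and the group-by-time interaction as the test. The pre-post correlation ρ is not given, so it is varied.

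**Step 1: can 28 be reproduced?** Not uniquely. With two groups and two times, the group-by-time F test is the square of the two-sample t test on change scores, with 26 error df and noncentrality λ = n·d²/2, where n is the number per group and d is the difference in SDs of change. A paired test has λ = n·dz². Solving each for 80% power:

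| Reading of the VAS sentence | Standardised effect at 80% power | SD of change that fits 2 points |
|---|---|---|
| Between-group difference in change, 14 vs 14 | d = 1.100 | 2/1.100 = 1.82 |
| Paired, all 28 pooled | dz = 0.549 | 2/0.549 = 3.64 |
| Paired, one arm of 14 | dz = 0.810 | 2/0.810 = 2.47 |

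Other settings also give 28. One is a G*Power within-between analysis with f = 0.25 and ρ = 0.6. So 28 is not shown to be wrong, but no reading can be picked out.

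The choice of reading matters. If the SD of change is 3.64, a 2-point between-group difference is d = 2/3.64 = 0.549, for which 14 per group have about 29% power. None of the readings concerns strength.

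**Step 2: what can 28 detect for one strength measure?** At alpha 0.05, 80% power needs d = 1.100 SD of change (λ = 14 × 1.100²/2 = 8.47). To express this in baseline SDs, use SD of change = baseline SD × √(2(1−ρ)).

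| ρ | √(2(1−ρ)) | Detectable, alpha 0.05 (baseline SDs) | Power for 0.5 baseline SD | Power for 0.8 baseline SD |
|---|---|---|---|---|
| 0.5 | 1.000 | 1.10 | 25% | 53% |
| 0.7 | 0.775 | 0.85 | 38% | 75% |
| 0.8 | 0.632 | 0.70 | 52% | 90% |
| 0.9 | 0.447 | 0.49 | 81% | over 99% |

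The range widens below ρ = 0.5: 1.30 baseline SDs at ρ = 0.3 and 1.56 at ρ = 0.

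**Step 3: if all three strength measures are primary.** At alpha 0.05/3 = 0.0167 each, 80% power needs d = 1.295 SD of change. Multiplying by the same factors gives 1.30, 1.00, 0.82 and 0.58 baseline SDs for ρ = 0.5, 0.7, 0.8 and 0.9.

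**The case against.** The best defence is that nothing here shows the trial to be too small. At ρ = 0.9, 28 patients detect about half a baseline SD in strength. That stands: a reader might infer that the trial is underpowered, or that 28 is an arithmetical error, and the documents support neither, because they give no strength effect, SD or correlation.

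A second defence is that the sample-size sentence refers to a repeated measures analysis, as the analysis section does, so it may have been a group-by-time calculation. That is possible. A reader might conclude from the pre-to-post wording that the calculation was certainly within-patient; the wording points that way but does not settle it. Either way the sized outcome is VAS, so the mismatch with the primary outcome remains.

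A reader might also infer that the primary outcome is undetermined, or that pain is the real primary because the hypothesis names it first. That is too strong. The Statistical Analysis section labels strength primary and VAS secondary, and the sample-size section labels nothing primary. Order in a list is weak evidence against an explicit label.

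Finally, the unranked strength measures and the reliance on main or interaction effects are partly separate matters of multiplicity and of what is being tested. They belong here only because power cannot be stated until the measure and the test are fixed.

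**Conclusion.** The point holds. The only power statement rests on VAS, the declared primary outcome is between-group muscle strength, and no power is given for it. This follows from the text alone and needs no assumption. Whether the VAS calculation was within-patient or between-group cannot be determined.

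The size of what 28 can detect does depend on assumptions. Under those listed in the working, it is about 1.1 SD of the change score for a single strength measure, or roughly 0.5 to 1.1 baseline SDs for ρ from 0.9 down to 0.5, and more for a lower ρ. If three measures share alpha, it is about 1.3 SD of the change score.

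It should be corrected because the primary test cannot be powered or interpreted until the measure and the effect are named, and doing so changes what the trial can conclude.

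**What to change.** Keep strength primary, as the Statistical Analysis section states. Before any between-group result is seen:

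1. Name one of the three strength measures as primary.
2. Name the group-by-time interaction as the primary test. A main effect of time or of group is not evidence that the groups responded differently.
3. Replace the power sentence with:

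> With 28 patients (14 per group), two-sided alpha 0.05 and complete data, the group-by-time test has 80% power for a between-group difference in change of about 1.1 SD of the change score (about 1.10, 0.85, 0.70 or 0.49 baseline SDs if the pre-post correlation is 0.5, 0.7, 0.8 or 0.9, and larger if it is lower, assuming equal SDs at both times). The number 28 was derived from a VAS calculation, which is not the power of the primary test.

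If all three strength measures stay primary, or if between-group results have already been seen, test the group-by-time interaction for each of the three at alpha 0.0167, state about 1.3 SD of the change score as the detectable difference, and keep the sentence saying that 28 came from VAS.

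Only if the primary label in the analysis section is itself the slip, and no between-group result has been seen, may one named VAS score (rest or activity) be made primary instead. The plan must then state the between-group difference, SD and correlation that give 28.

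**Cost.** No extra patients. Two strength measures become secondary, or alpha falls to 0.0167 for each of three. Main effects no longer count as primary evidence. The stated detectable effect may look less favourable, and the new sentence says what 28 can detect without justifying 28.
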